17. APPENDIX

17.1. APPENDIX 1: NATIONAL EARLY WARNING SCORE 2 (NEWS2)

The National Early Warning Score 2 (NEWS2) determines the degree of illness of a patient and prompts critical care intervention.

[figure not shown]
CONFIDENTIAL Page 103 of 108

Variable		Points
Respiratory rate, breaths per minute	≤8	3
	9-11	1
	12-20	0
	21-24	2
	≥25	3
	≤91%	3
SpO ₂ (on room air or	92-93%	2
supplemental)	94-95%	1
	≥96%	0
	≤83%	3
	84-85%	2
SpO ₂ (if patient has	86-87%	1
hypercapnic respiratory failure)	88-92%, ≥93% on room air	0
	93-94% on supplemental oxygen	1
	95-96% on supplemental oxygen	2
	≥97% on supplemental oxygen	3
Room air or supplemental oxygen	Supplemental oxygen	2
	Room air	0
Temperature	≤35.0°C (95°F)	3
	35.1-36.0°C (95.1-96.8°F)	1
	36.1-38.0°C (96.9-100.4°F)	0
	38.1-39.0°C (100.5-102.2°F)	1
	≥39.1°C (102.3°F)	2
Systolic BP, mmHg	≤90	3

[figure not shown]
CONFIDENTIAL Page 104 of 108

	91-100	2
	101-110	1
	111-219	0
	≥220	3
Pulse, beats per minute	≤40	3
	41-50	1
	51-90	0
	91-110	1
	111-130	2
	≥131	3
Consciousness	Alert	0
	New-onset confusion (or disorientation/agitation), responds to voice, responds to pain, or unresponsive	3

CONFIDENTIAL Page 105 of 108

[figure not shown]

17.2. APPENDIX 2: COMMON TERMINOLOGY CRITERIA FOR ADVERSE EVENTS V5.03

For complete detailed information please refer to the link below:

 $https://ctep.cancer.gov/protocoldevelopment/electronic_applications/docs/CTCAE_v5_Quick_Reference_5x7.pdf$

CONFIDENTIAL Page 106 of 108

[figure not shown]
17.3. APPENDIX 3: SEQUENTIAL ORGAN FAILURE ASSESSMENT (SOFA) SCORE

Predicts ICU mortality based on lab results and clinical data

Variable	Points
PaO ₂ /FiO ₂ , mmHg	
≥400	0
300-399	+1
200-299	+2
100-199 and mechanically ventilated	+3
<100 and mechanically ventilated	+4
Platelets, $\times 10^3/\mu L$	
≥150	0
100-150	+1
50-99	+2
20-49	+3
<20	+4
Glasgow Coma Scale	
15	0
13–14	+1
10–12	+2
6–9	+3
<6	+4
Bilirubin, mg/dL (μmol/L)	
<1.2 (<20)	0
1.2–1.9 (20-32)	+1
2.0–5.9 (33-101)	+2
6.0–11.9 (102-204)	+3
≥12.0 (>204)	+4

Mean arterial pressure OR administration of vasoactive agents required (listed doses are in units of mcg/kg/min)

CONFIDENTIAL Page 107 of 108

No hypotension	0	
MAP < 70 mmHg	+1	
DOPamine ≤5 or DOBUTamine (any dose)	+2	
DOPamine >5, EPINEPHrine ≤0.1, or norEPINEPHrine ≤0.1	+3	
DOPamine >15, EPINEPHrine >0.1, or norEPINEPHrine >0.1	+4	
Creatinine, mg/dL (µmol/L) (or urine output)		
<1.2 (<110)	0	
1.2–1.9 (110-170)	+1	
2.0–3.4 (171-299)	+2	
3.5–4.9 (300-440) or UOP <500 mL/day)	+3	
≥5.0 (>440) or UOP <200 mL/day	+4	

CONFIDENTIAL Page 108 of 108

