3.3.2. Exclusion Criteria

Potential subjects meeting any of the following criteria will be excluded from enrollment:

- 1. Subjects with do-not-resuscitate (DNR) and/or do-not-intubate (DNI) orders or expected to be made DNR/DNI in setting of resource limitations or family wishes.
- 2. Not a candidate for dialysis or continuation of care (or full medical support) in setting of resource limitations.
- 3. Subject on continuous vasopressors (at the dose of norepinephrine >20µg/min and/or vasopressin >0.04 units/kg/min) for >48 hours at time of screening.
- 4. Subjects who have a history of allergic reactions attributed to compounds of similar chemical or biologic composition to leronlimab (PRO 140) are not eligible.
- 5. Inability to provide informed consent or to comply with test requirements
- 6. Consideration by the investigator, for safety reasons, that the subject is an unsuitable candidate to receive study treatment
- 7. Pregnancy or breast feeding
- 8. Subject participating in another study with for an investigational treatment for COVID-19.

Note: Subject who were prescribed (1) hydroxychloroguine or chloroguine with or without azithromycin, (2) Remdesivir, (3) convalescent plasma therapy, or (4) immunomodulatory treatments (including but not limited to sarilumab, clazakizumab, tocilizumab, and anakinra) for the off-label treatment of COVID-19 prior to study enrollment may be included and may continue to receive these agents as part of standard-of-care.

CONFIDENTIAL Page 47 of 108

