Assessment for the requirement of: Mechanical Ventilation, Non- Invasive Ventilation, Supplemental Oxygen, Vasopressors Use, Renal Replacement Therapy, ICU Admission and Hospital Stay	Х	х		х	х	х		
Assessment for any new infections		X		X	X	X		
Mortality Status						X	X	X
Concomitant Medications	X	X	X	X	X	X	X	X
Adverse Events			X	X	X	X	X	X

- [1] Informed consent must be obtained prior to patient participation in any protocol-related activities that are not part of routine care.
- [2] Initial evaluation of patient eligibility will be performed by Investigator.
- [3] Medical history and current therapies (medications and non-medications).
- [4] Symptom-directed physical examination
- [5] Post treatment vital signs will be recorded at V2, V4, V5 (EOT) and will include blood pressure, heart rate, respiration rate, and temperature.

CONFIDENTIAL Page 52 of 108

Date: 28-Dec-2020

- [6] The SOFA score assessment will be based on PaO2/FiO2, platelets, Glasgow coma scale (GCS), bilirubin, Mean arterial pressure OR administration of vasoactive agents required, and creatine.
- [7] National Early Warning Score 2 (NEWS2) Assessment is based on 7 clinical parameters (respiration rate, oxygen saturation, any supplemental oxygen, temperature, systolic blood pressure, heart rate, level of consciousness)
- [8] Based on hospital discharge or normalization of fever, respiratory rate, alleviation of cough, and resolution of hypoxia.
- [9] Hemoglobin, Hematocrit (HCT), Red Blood Cells (RBC), White Blood Cells (WBC) with total and differential count, Absolute Neutrophil Count (ANC) and platelets.
- [10] Biochemistry

Hepatic function indicators: total bilirubin, alkaline phosphatase, aspartate aminotransferase (AST), alanine aminotransferase (ALT), total protein, albumin Lactate dehydrogenase (LDH)

Renal function indicators: Serum creatinine, creatinine clearance, or eGFR

Electrolytes: sodium, potassium, chloride, calcium and bicarbonate

Other: glucose (random), cholesterol (total), Creatine kinase, C-reactive protein, serum ferritin, d-dimer

- [11] Prothrombin time (PT) and International Normalized Ratio (INR)
- [12] ONLY performed on women of childbearing potential.
- [13] Urine samples will be tested for color, appearance, specific gravity, pH, protein, glucose, occult blood, ketones, leukocyte esterase, nitrite, bilirubin, urobilinogen, and microscopic examination of urine sediment.

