7.14. SEQUENTIAL ORGAN FAILURE ASSESSMENT (SOFA) SCORE

The SOFA score assessment will be based on PaO2/FiO2, platelets, Glasgow coma scale (GCS), bilirubin, Mean arterial pressure OR administration of vasoactive agents required, and creatine (See Appendix 17.3)

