### 9.2.3 Exploratory Outcome Measures (Endpoints)

## 9.2.3.1 All-Cause Mortality at Day 42

All-cause mortality at Day 42 will be summarized descriptively by treatment group. Similar analysis methods used for the primary endpoint will be applied to analyze the data from this endpoint

9.2.3.2 Change in clinical status of subject at Days 3 and 7 (on a 7 point ordinal scale)

Change in clinical status of subject at Days 3 and 7 will be summarized descriptively and compared using ANCOVA adjusting for stratification factors.

If the Normality assumption is not met, a non-parametric method or a rank –ANCOVA analysis i.e., an ANCOVA analysis on rank-transformed data will be used.

9.2.3.3 Change from baseline in Sequential Organ Failure Assessment (SOFA) score at Days 3 and 7

Change from baseline in Sequential Organ Failure Assessment (SOFA) score at Days 3 and 7 will be summarized descriptively and compared using ANCOVA adjusting for stratification factors. If the Normality assumption is not met, a non-parametric method or a rank –ANCOVA analysis i.e., an ANCOVA analysis on rank-transformed data will be used.

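### The SOFA renal item has no entry for dialysis, so unless a low urine output is recorded, a subject on renal replacement therapy can score as improved or unchanged

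*Protocol*

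**What the plan says.** Protocol Appendix 17.3 scores the renal item on creatinine, with "or urine output" as the alternative. Urine output enters only in the two highest rows: below 500 mL/day gives +3, and the +4 row is "≥5.0 (>440) or UOP <200 mL/day". RRT appears nowhere in the table.

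Protocol Section 7.14 lists the last two SOFA inputs as "Mean arterial pressure OR administration of vasoactive agents required, and creatine" and refers to the appendix. Footnote 6 of Table 4-2 gives the same inputs. Table 4-2 has a urinalysis row but none for urine volume.

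RRT is recorded. The support row of Table 4-2, which ends "Renal Replacement Therapy, ICU Admission and Hospital Stay", is marked at V1 to V5, so it covers every SOFA visit (V2 to V5). New RRT is an exploratory endpoint in its own right (Protocol 8.2.3, SAP 9.2.3.14).

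For the analysis, SAP 9.2.3.3 says "Change from baseline in Sequential Organ Failure Assessment (SOFA) score at Days 3 and 7 will be summarized descriptively and compared using ANCOVA", with rank-ANCOVA if normality fails. SAP 9.2.3.7 says the same for Day 14. Neither section, nor the data conventions in SAP Section 8, says how SOFA is scored during RRT. Table 4-2 and Protocol 4.2.1 to 4.2.3 label the SOFA assessment as applying if the subject is intubated.

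**The concern.** The table mostly credits organ support as well as the measured value. Vasoactive drugs earn +2 to +4, and the two highest respiratory rows require mechanical ventilation. The renal item does not: it reads creatinine even when dialysis has lowered it. A subject whose kidneys have failed can therefore move down the table because treatment for that failure has begun. The same subject can count as a new RRT event under SAP 9.2.3.14 and as improved or unchanged under SAP 9.2.3.3 or 9.2.3.7.

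At stake is the direction of an organ-failure comparison. If one arm has more new RRT, the scoring works in that arm's favour.

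**Working it through.** The plan states no figure on this point, so there is nothing to reproduce. The check scores the table as printed.

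**Inputs from Appendix 17.3 (creatinine in mg/dL).** Below 1.2 = 0; 1.2–1.9 = +1; 2.0–3.4 = +2; 3.5–4.9 or urine output below 500 mL/day = +3; 5.0 and above or urine output below 200 mL/day = +4.

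**Assumptions.** The creatinine values before and during dialysis are illustrative. Urine output is held the same at both visits. The table does not say which criterion governs when the two disagree, so the higher is taken:

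renal score = max(creatinine score, urine-output score); change = score on RRT − score before.

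| Creatinine before → on RRT | Output not recorded, or 800 mL/day | 300 mL/day | 100 mL/day |
|---|---|---|---|
| 5.5 → 3.0 | 4 → 2 (−2) | 4 → 3 (−1) | 4 → 4 (0) |
| 5.5 → 1.8 | 4 → 1 (−3) | 4 → 3 (−1) | 4 → 4 (0) |
| 5.5 → 1.1 | 4 → 0 (−4) | 4 → 3 (−1) | 4 → 4 (0) |
| 4.0 → 1.8 | 3 → 1 (−2) | 3 → 3 (0) | 4 → 4 (0) |
| 4.0 → 1.1 | 3 → 0 (−3) | 3 → 3 (0) | 4 → 4 (0) |
| 2.5 → 1.1 | 2 → 0 (−2) | 3 → 3 (0) | 4 → 4 (0) |

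The spurious fall ranges from 0 to 4 points. A recorded output below 200 mL/day removes it, and one below 500 mL/day limits it to 1 point in these examples. The full effect needs an output that is higher or not recorded.

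**No-change case.** Creatinine 1.6 before (+1) and 1.8 on new dialysis (+1) gives a change of 0. With the item set to +4 during RRT, the change is 4 − 1 = +3. A subject on RRT at both baseline and follow-up would score 4 − 4 = 0, so existing RRT is not counted as worsening.

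**Arm level.** The shift in the difference between arm means is the difference between arms in the average under-scoring. That depends on how many subjects in each arm start RRT and how far each is under-scored. The documents give neither, so no figure follows.

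**Two smaller gaps in the same table.**
- Platelets: the 0 row starts at 150 and the +1 row runs from 100 to 150. Among whole-number counts from 0 to 399, 150 is the only one that falls in two rows.
- Vasopressin: the vasoactive rows, such as "DOPamine >5, EPINEPHrine ≤0.1, or norEPINEPHrine ≤0.1", name dopamine, dobutamine, epinephrine and norepinephrine only. Exclusion criterion 3 ("vasopressin >0.04 units/kg/min") and the stratum definition in Protocol 8.5 both treat vasopressin as a vasopressor.

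**The case against.** The strongest reply is that the quoted row already protects the score: a dialysed subject passing less than 200 mL/day stays at +4 whatever happens to creatinine. That is correct, and it limits the point to subjects whose output is higher or not recorded.

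A reader might infer that the item rests on creatinine alone, because 7.14 and footnote 6 name nothing else and the schedule has no urine-volume row. The documents do not go that far. Section 7.14 refers to the appendix, which includes urine output. The Glasgow Coma Scale and mean arterial pressure are also SOFA inputs without a row of their own in Table 4-2. What stands is that nothing requires urine output to be recorded, and nothing says which criterion governs.

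A reader might also infer that a subject on vasopressin alone scores 0. The table is silent rather than assigning 0: a subject who needs a drug to hold pressure is not plainly free of hypotension, and +1 applies if mean arterial pressure is below 70 mmHg. Nor do the documents support any particular value for vasopressin. Placing it at +3, for example, would still show a fall from +4 when it replaces norepinephrine above 0.1.

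Finally, new RRT is reported separately, so a difference between arms would be visible. That helps a reader to interpret the SOFA result but does not correct the score.

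**Conclusion.** The point holds in a limited form. As printed, the renal item can fall by up to 4 points, or stay flat, in a subject on RRT unless a urine output below 500 mL/day is recorded. This rests on dialysis lowering creatinine and on the higher of the two criteria being used.

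The bias favours an arm with more new RRT. It needs RRT to start unequally between the arms, and subjects already on RRT at baseline partly cancel in a change score. It is tempting to multiply an assumed RRT rate by an assumed under-scoring to get a shift in arm means, but the documents supply neither input. Under rank-ANCOVA a shift in means would not be the relevant measure anyway.

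The reach is small. SOFA change is exploratory at Days 3, 7 and 14 (Protocol 8.2.3, SAP 3.3), and the schedule collects it only in intubated subjects. Day 28 mortality and the secondary endpoints are untouched. The platelet overlap is one value and one point, and the vasopressin gap is a missing convention. This is a worthwhile repair, not a threat to the trial's conclusions.

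**What to change.** 1. In Appendix 17.3 and SAP 9.2.3.3 and 9.2.3.7, derive the renal item as +4 at any visit at which RRT is recorded, in the same way at baseline and in both arms. Table 4-2 and Protocol 4.2.1 take the RRT record at V2, but Section 7.20 omits V2 from its list. Align 7.20 so that the baseline status is clear.
2. Report the score as printed as a sensitivity analysis, stating whether urine output was available and which criterion governed.
3. Change the platelet +1 row to 100–149.
4. State one scoring convention for vasopressin before unblinding. The choice matters less than fixing it in advance.

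The cost is a few lines in the appendix and SAP and a few lines of derivation code. RRT and vasopressor use are already recorded at V2 to V5, so no new data are needed. The downside is a small departure from the printed table, which must be stated when the score is reported.

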# LIST OF ABBREVIATIONS

AE Adverse Event ALT Alanine Transaminase ASA American Statistical Association AST Aspartate Aminotransferase BMI Body Mass Index COVID-19 Coronavirus Disease 2019 CRF Case Report Form CS Clinically Significant DSMC Data Safety Monitoring Committee ECG Electrocardiogram ECMO Extracorporeal Membrane Oxygenation EOT End of Treatment eCRF Electronic Case Report Form FDA U.S. Food and Drug Administration FU Follow-Up HEENT Head, Ears, Eyes, Nose, Throat IA Interim Analysis ICF Informed Consent Form ICH International Conference on Harmonization ICU Intensive Care Unit IP Investigational Product ITT Intent-to-treat
ASA American Statistical Association AST Aspartate Aminotransferase BMI Body Mass Index COVID-19 Coronavirus Disease 2019 CRF Case Report Form CS Clinically Significant DSMC Data Safety Monitoring Committee ECG Electrocardiogram ECMO Extracorporeal Membrane Oxygenation EOT End of Treatment eCRF Electronic Case Report Form FDA U.S. Food and Drug Administration FU Follow-Up HEENT Head, Ears, Eyes, Nose, Throat IA Interim Analysis ICF Informed Consent Form ICH International Conference on Harmonization ICU Intensive Care Unit IP Investigational Product
AST Aspartate Aminotransferase BMI Body Mass Index COVID-19 Coronavirus Disease 2019 CRF Case Report Form CS Clinically Significant DSMC Data Safety Monitoring Committee ECG Electrocardiogram ECMO Extracorporeal Membrane Oxygenation EOT End of Treatment eCRF Electronic Case Report Form FDA U.S. Food and Drug Administration FU Follow-Up HEENT Head, Ears, Eyes, Nose, Throat IA Interim Analysis ICF Informed Consent Form ICH International Conference on Harmonization ICU Intensive Care Unit IP Investigational Product
AST Aspartate Aminotransferase BMI Body Mass Index COVID-19 Coronavirus Disease 2019 CRF Case Report Form CS Clinically Significant DSMC Data Safety Monitoring Committee ECG Electrocardiogram ECMO Extracorporeal Membrane Oxygenation EOT End of Treatment eCRF Electronic Case Report Form FDA U.S. Food and Drug Administration FU Follow-Up HEENT Head, Ears, Eyes, Nose, Throat IA Interim Analysis ICF Informed Consent Form ICH International Conference on Harmonization ICU Intensive Care Unit IP Investigational Product
BMI Body Mass Index COVID-19 Coronavirus Disease 2019 CRF Case Report Form CS Clinically Significant DSMC Data Safety Monitoring Committee ECG Electrocardiogram ECMO Extracorporeal Membrane Oxygenation EOT End of Treatment eCRF Electronic Case Report Form FDA U.S. Food and Drug Administration FU Follow-Up HEENT Head, Ears, Eyes, Nose, Throat IA Interim Analysis ICF Informed Consent Form ICH International Conference on Harmonization ICU Intensive Care Unit IP Investigational Product
COVID-19 CRF Case Report Form CS Clinically Significant DSMC Data Safety Monitoring Committee ECG Electrocardiogram ECMO Extracorporeal Membrane Oxygenation EOT End of Treatment eCRF Electronic Case Report Form FDA U.S. Food and Drug Administration FU Follow-Up HEENT Head, Ears, Eyes, Nose, Throat IA Interim Analysis ICF Informed Consent Form ICH International Conference on Harmonization ICU Intensive Care Unit IP Investigational Product
CS Clinically Significant  DSMC Data Safety Monitoring Committee  ECG Electrocardiogram  ECMO Extracorporeal Membrane Oxygenation  EOT End of Treatment  eCRF Electronic Case Report Form  FDA U.S. Food and Drug Administration  FU Follow-Up  HEENT Head, Ears, Eyes, Nose, Throat  IA Interim Analysis  ICF Informed Consent Form  ICH International Conference on Harmonization  ICU Intensive Care Unit  IP Investigational Product
DSMC Data Safety Monitoring Committee ECG Electrocardiogram ECMO Extracorporeal Membrane Oxygenation EOT End of Treatment eCRF Electronic Case Report Form FDA U.S. Food and Drug Administration FU Follow-Up HEENT Head, Ears, Eyes, Nose, Throat IA Interim Analysis ICF Informed Consent Form ICH International Conference on Harmonization ICU Intensive Care Unit IP Investigational Product
ECG Electrocardiogram  ECMO Extracorporeal Membrane Oxygenation  EOT End of Treatment  eCRF Electronic Case Report Form  FDA U.S. Food and Drug Administration  FU Follow-Up  HEENT Head, Ears, Eyes, Nose, Throat  IA Interim Analysis  ICF Informed Consent Form  ICH International Conference on Harmonization  ICU Intensive Care Unit  IP Investigational Product
ECG Electrocardiogram ECMO Extracorporeal Membrane Oxygenation EOT End of Treatment eCRF Electronic Case Report Form FDA U.S. Food and Drug Administration FU Follow-Up HEENT Head, Ears, Eyes, Nose, Throat IA Interim Analysis ICF Informed Consent Form ICH International Conference on Harmonization ICU Intensive Care Unit IP Investigational Product
EOT End of Treatment eCRF Electronic Case Report Form FDA U.S. Food and Drug Administration FU Follow-Up HEENT Head, Ears, Eyes, Nose, Throat IA Interim Analysis ICF Informed Consent Form ICH International Conference on Harmonization ICU Intensive Care Unit IP Investigational Product
eCRF Electronic Case Report Form  FDA U.S. Food and Drug Administration  FU Follow-Up  HEENT Head, Ears, Eyes, Nose, Throat  IA Interim Analysis  ICF Informed Consent Form  ICH International Conference on Harmonization  ICU Intensive Care Unit  IP Investigational Product
FDA U.S. Food and Drug Administration FU Follow-Up HEENT Head, Ears, Eyes, Nose, Throat IA Interim Analysis ICF Informed Consent Form ICH International Conference on Harmonization ICU Intensive Care Unit IP Investigational Product
FU Follow-Up HEENT Head, Ears, Eyes, Nose, Throat IA Interim Analysis ICF Informed Consent Form ICH International Conference on Harmonization ICU Intensive Care Unit IP Investigational Product
HEENT Head, Ears, Eyes, Nose, Throat  IA Interim Analysis  ICF Informed Consent Form  ICH International Conference on Harmonization  ICU Intensive Care Unit  IP Investigational Product
IA Interim Analysis ICF Informed Consent Form ICH International Conference on Harmonization ICU Intensive Care Unit IP Investigational Product
ICF Informed Consent Form ICH International Conference on Harmonization ICU Intensive Care Unit IP Investigational Product
ICH International Conference on Harmonization ICU Intensive Care Unit IP Investigational Product
ICU Intensive Care Unit IP Investigational Product
IP Investigational Product
ITT Intent-to-treat
LOA Letter of Amendment
MedDRA Medical Dictionary for Regulatory Activities
mITT Modified Intent-to-Treat
PI Principal Investigator
PP Per Protocol
PT Preferred Term
RRT Renal Replacement Therapy
SAE Serious Adverse Event
SAP Statistical Analysis Plan
SC Subcutaneous
SOC System Organ Class
SOFA Sequential Organ Failure Assessment
SOP Standard Operating Procedure
SpO 2 Peripheral Capillary Oxygen Saturation

SV

Screening Visit

**TEAE** 

Treatment Emergent Adverse Events

TV

Treatment Visit

WHO

World Health Organization

#### 1. INTRODUCTION

This Statistical Analysis Plan describes the planned analyses and reporting for the clinical trial protocol CD12\_COVID-19, sponsored by CytoDyn Inc. The reader of this Statistical Analysis Plan (SAP) is encouraged to review the complete protocol and amendments as this plan contains only a limited overview of protocol information. The main objective of this plan is to provide details pertaining to statistical methodology, data conventions, and processes used for the analysis of data from this trial.

The format and content of this Statistical Analysis Plan are structured to provide sufficient detail to meet the requirements specified by the International Conference on Harmonization (ICH) E9: Guidance on Statistical Principles in Clinical Trials. All work planned and presented in this Statistical Analysis Plan will follow the ethical guidelines published by the American Statistical Association (ASA).

The following documents and references [1-6], were reviewed in preparation of this Statistical Analysis Plan:

- Protocol Version 6.0 / 28-Dec-2020
- US Federal Register, Department of Health and Human Services, FDA, Guidance on Statistical Principles for Clinical Trials (1998)
- ASA Ethical Guidelines for Statistical Practice (2016)
- The Royal Statistical Society: Code of Conduct (2014)
- ICH Guidance on the Structure and Content of Clinical Study Reports (ICH E3(R1), 2013)
- ICH Guidance on the Statistical Principles for Clinical Trials (ICH E9(R1), 2017)

